### 7.4 Immunogenicity and Other Immunology Analyses

All immunogenicity analyses will be based on subjects who received at least one dose of study vaccine (AERAS-404, BCG, or placebo). Immunogenicity will be summarized for all time points as collected and as available for the Safety & Immunogenicity Cohort, or for all subjects. No imputation for missing data will be performed. Data will be transformed as appropriate prior to analysis.

Additional analyses may be performed based on subjects who complete all scheduled vaccinations with study vaccine (per-protocol population).

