### 5.2. SAFETY ANALYSIS SET

The Safety analysis set is defined as all participants included in the Randomized analysis set who received at least one dose of study vaccination (H4:IC31, Placebo or BCG).

---

Document: Aeras\_C-040-404\_SAP\_V2\_0  
Author: [name]

Version Number: 2.0  
Version Date: 29SEP2017

Template No: CS\_TP\_BS016 – Revision 3  
Effective Date: 01May2012

Reference: CS\_WI\_BS005

A participant will be included in the Safety analysis set if the participant:

- Is included in the Randomized analysis set.
- AND
- Has at least one date of study vaccination in the database as recorded on the Exposure (Day 0) or Exposure (Day 56) eCRF.

For analyses and presentations based on the Safety analysis set, participants will be analyzed according to the treatment received regardless of the treatment allocated (that is 'as treated'):

- For all presentations, including by dose at onset presentations, participants who received a different treatment to that allocated, but the same consistent treatment for all relevant doses, analyze and present participants according to the treatment received (both overall and per dose at onset).
- Participants who received a different treatment to that allocated, but not the same consistent treatment for all relevant doses (mixed treatment regimen), will be analyzed as described below:
  - o For all presentations, with the exception of by dose at onset presentations, analyze and present participants according to the following vaccine hierarchy: H4:IC31 followed by BCG and then placebo.
  - o For all by dose at onset presentations, analyze participants according to the treatment received for each dose at onset; therefore, participants are analyzed and presented according to different treatments per the relevant doses.

The Safety analysis set will be used as the primary analysis set for all safety and immunogenicity analyses.

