### 5.3. MODIFIED INTENT-TO-TREAT ANALYSIS SET

The Modified Intent-to-treat analysis set is defined as all participants included in the Safety analysis set who had a negative QFT-GIT test result at Day 84.

A participant will be programmatically included in the Modified Intent-to-treat analysis set if the participant:

- Is included in the Safety analysis set.
- AND
- Has a negative QFT-GIT test result at the Day 84 visit.

For analyses and presentations based on the Modified Intent-to-treat analysis set, participants will be analyzed according to the treatment assigned regardless of the treatment received.

The Modified Intent-to-treat analysis set will be used for efficacy analyses.

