## 15. IMMUNOGENICITY

### 15.1. PERIPHERAL BLOOD MONONUCLEAR CELLS (PBMC) INTRACELLULAR CYTOKINE STAINING (ICS)

The following tables are planned for presentation (based on the Safety analysis set, in the Safety and Immunogenicity Cohort):

- Percent antigen-specific T cell negative control-subtracted ANY cytokine response and change from Baseline.
  - o Only the derived ANY cytokine combination will be included in this table.
  - o This table will include descriptive statistics and 95% confidence interval (CI) for the median based on order statistics at each applicable visit as well as the change from Baseline per T cell and stimulation antigen (including a 'total' stimulation antigen for Ag85B and TB10.4 combined).
  - o This table will be repeated for the negative-control ANY cytokine combination.
- Percent antigen-specific T cell negative-control subtracted Positive (G,2) cytokine response and change from Baseline.
  - o Only the derived Positive (G,2) cytokine combination will be included in this table.
  - o This table will include descriptive statistics and 95% confidence interval (CI) for the median based on order statistics at each applicable visit as well as the change from Baseline per T cell and stimulation antigen (including a 'total' stimulation antigen).
  - o This table will be repeated for the negative control Positive (G,2) cytokine combination.
- Number (percentage) of responders based on the derived Positive (G,2) cytokine combination.
  - o This is to include the number and percentage of responders (Refer to Section 15.1.2: Responder Status) at each visit per T cell and stimulation antigen.
  - o Percentages are based on the number of participants in the Safety analysis set within each treatment group with data available to determine responder status.
  - o P-values are also to be included and are based on a Fisher's EXACT test comparing each of the treatment groups.
- Comparisons of median negative control-subtracted ANY cytokine response.
  - o Only the derived ANY cytokine combination will be included in this table.
  - o This table will include the number of participants who have a negative control-subtracted negative-set-to-zero value available as well as the median of these values.
  - o P-values based on the Wilcoxon-Mann Whitney test for pair-wise comparisons between treatment groups will be performed.
- Comparisons of median negative control-subtracted Positive (G,2) cytokine response.

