  - o Only the derived Positive (G,2) cytokine combination will be included in this table.
  - o This table will include the number of participants who have a negative control-subtracted negative-set-to-zero value available as well as the median of these values.
  - o P-values based on the Wilcoxon-Mann Whitney test for pair-wise comparisons between treatment groups will be performed.

---

Document: Aeras\_C-040-404\_SAP\_V2\_0  
Author: [name]

Version Number: 2.0  
Version Date: 29SEP2017

Template No: CS\_TP\_BS016 – Revision 3  
Effective Date: 01May2012

Reference: CS\_WI\_BS005

The following figures are planned for presentation (based on the Modified Intent-to-treat analysis set):

- Antigen-specific negative control-subtracted ANY cytokine response:
  - o Dot plot of antigen-specific negative control-subtracted ANY cytokine response per study day.
  - o One figure will be prepared for each stimulation antigen, including the derived total (Ag85B and TB10.4) stimulation antigen response; the median response will be represented by a horizontal line per treatment group and study day.
  - o Separate plots will be created per T cell (CD4+/CD8+).
  - o This figure will be repeated for the negative control ANY cytokine combination.
  - o Different symbols will be used to differentiate between responders (closed circles), non-responders (cross) and missing responder status (triangle) as based on the derived Positive (G,2) cytokine combination responder status.
- Antigen-specific negative control-subtracted Positive (G,2) cytokine response:
  - o Dot plot of antigen-specific negative control-subtracted Positive (G,2) cytokine response per study day.
  - o One figure will be prepared for each stimulation antigen, including the derived total (Ag85B and TB10.4) stimulation antigen response; the median response will be represented by a horizontal line per treatment group and study day.
  - o Separate plots will be created per T cell (CD4+/CD8+).
  - o This figure will be repeated for the negative control Positive (G,2) cytokine combination.
  - o Different symbols will be used to differentiate between responders (closed circles), non-responders (cross) and missing responder status (triangle) as based on the derived Positive (G,2) cytokine combination responder status.
- Antigen-specific negative control-subtracted ANY cytokine median response:

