    - CD4+: IFN-g, IL-2, IL-17, IL-22.
    - CD8+: IFN-g, IL-2, TNF, CD107a.
  - o Dot plot of participants' negative control-subtracted cytokine response per single-gate on the left hand side. Dot plot of participants' negative control-subtracted ANY cytokine response on the right hand side. The median response will be represented by a horizontal line per treatment group and cytokine combination.
  - o These figures will be repeated for the negative control.

The following listings are planned for presentation (based on the Safety analysis set):

- Percent antigen-specific T cell negative control-subtracted cytokine response and change from Baseline:
  - o Only derived cytokine combinations will be included in this listing.
- Percent antigen-specific T cell negative control-subtracted ANY cytokine response and total (Ag85B and TB10.4) vaccine response:
  - o Only derived cytokine combinations will be included in this listing.
- ICS responder status based on the Positive (G,2) response:
  - o The responder status for each antigen will be displayed, including the overall status.

The following PBMC ICS variables, as presented in the planned TLF shells, will be contained in the data received from Aeras:

- Stimulation antigen:
  - o Ag85B.
  - o BCG.
  - o TB10.4.
  - o Negative control:
    - DMSO for Ag85B and TB10.4.
    - R10 for BCG.
- T cell:
  - o CD4+.
  - o CD8+.
- Cell counts and percentages (including a total cell count) for each possible combination (alone and in combination with all other cytokines) of the following cytokines per stimulation antigen, study day and participant:
  - o IFN- $\gamma$  (+/-).
  - o TNF (+/-).
  - o IL-2 (+/-).
  - o IL-17A (+/-).
  - o IL-22 (+/-).
  - o CD154 (+/-).
  - o CD107a (+/-).

Document: Aeras\_C-040-404\_SAP\_V2\_0

Author: [name]

Version Number:

2.0

Version Date:

29SEP2017

Template No: CS\_TP\_BS016 – Revision 3

Reference: CS\_WI\_BS005

Effective Date: 01May2012

Copyright © 2012 Quintiles Transnational Corp. All rights reserved.

The contents of this document are confidential and proprietary to Quintiles Transnational Corp. Unauthorized use, disclosure or reproduction is strictly prohibited.

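### The PBMC ICS figures are on the modified ITT set while the ICS tables and listings are on the Safety set, so the plots omit a few tabulated participants (minor)

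*SAP*

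**What the plan says.** SAP 5.2 sets the rule for immunogenicity: "The Safety analysis set will be used as the primary analysis set for all safety and immunogenicity analyses". Protocol 7.4 agrees: "All immunogenicity analyses will be based on subjects who received at least one dose of study vaccine". Neither places any condition on a later QFT-GIT result.

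SAP 5.3 defines the modified ITT set as "all participants included in the Safety analysis set who had a negative QFT-GIT test result at Day 84" and states its use: "The Modified Intent-to-treat analysis set will be used for efficacy analyses". It is analysed by treatment assigned; the Safety set is analysed by treatment received.

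Within SAP 15.1 the population depends on the type of output:

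- Tables: "The following tables are planned for presentation (based on the Safety analysis set, in the Safety and Immunogenicity Cohort".
- Figures: "The following figures are planned for presentation (based on the Modified Intent-to-treat analysis set".
- Listings: "The following listings are planned for presentation (based on the Safety analysis set".

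The figures covered are the dot plots with medians and responder symbols, the median line plots with quartile bars, the stacked bars and the polyfunctional profile plots. The whole blood ICS tables and listings in SAP 15.2 are on the Safety set. SAP 15.1 gives no reason for treating the PBMC figures differently.

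**The concern.** The figures and tables show the same assay at the same visits, and a reader will set a plotted median beside the tabulated one. As written, they need not agree, for two reasons.

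First, the figures drop participants on a test result that comes after every ICS sample has been drawn. Even the Day 0 points are filtered on what happened at Day 84. The protocol's reason for the Day 84 wash-out (Protocol 2.2) concerns the analyses of prevention of infection; it is not extended to immunogenicity.

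Second, the treatment grouping differs. Anyone given the wrong product could be plotted in one arm and tabulated in another.

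At stake is consistent presentation of a secondary objective. No efficacy result depends on it.

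**Working it through.** The plan gives no figure for this point, so there is nothing to reproduce. Three checks follow.

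**1. The populations side by side (SAP 5.2, 5.3, 15.1)**

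| PBMC ICS output | Set | Negative Day 84 QFT-GIT required | Grouping | Cohort named in heading |
|---|---|---|---|---|
| Tables | Safety | No | As treated | Yes |
| Listings | Safety | No | As treated | No |
| Figures | Modified ITT | Yes | As assigned | No |

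ICS is done only in the 90-person Safety and Immunogenicity Cohort, at Day 0 and Day 70 (Protocol Table 3-3). Because the modified ITT set is a subset of the Safety set, the figures can only lose people relative to the tables.

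**2. Does the Day 84 test always follow the Day 70 sample? (windows in Protocol Appendix A)**

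- BCG: latest Day 70 visit is 70 + 5 = Day 75; earliest Day 84 visit is 84 - 7 = Day 77.
- AERAS-404 and placebo: latest Day 70 visit is 14 + 3 = 17 days after Day 56; earliest Day 84 visit is 28 - 5 = 23 days after Day 56.

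For visits within window, it does.

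**3. How many would be dropped?**

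Inputs: 10% conversion per year as the planning rate, 17% as the site's own experience (read as per year, consistent with the 14-17% per year in Protocol 1.1), and 7% per year loss to follow-up (Protocol 7.6); 90 participants, 30 per arm (Protocol Table 2-1). Proportion converting by Day 84 = 1 - (1 - annual rate)^(84/365.25).

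- At 10%: 1 - 0.90^(84/365.25) = 2.39%, so 2.2 of 90, or 0.7 of 30.
- At 17%: 1 - 0.83^(84/365.25) = 4.19%, so 3.8 of 90, or 1.3 of 30.
- Counting from the start of the 21-day screening window (105 days): 2.98% and 5.22%, so 2.7 and 4.7 of 90.
- Chance of at least one Day 84 converter among 90, taking participants as independent (84 days): 1 - (1 - 0.0239)^90 = 0.89 and 1 - (1 - 0.0419)^90 = 0.98.

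Participants with no Day 84 result are also outside the modified ITT set. At 7% per year:

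- Lost between Day 0 and Day 84: 1 - 0.93^(84/365.25) = 1.65%, or 1.5 of 90. This bears on the Day 0 points.
- Lost between Day 70 and Day 84: 1 - 0.93^(14/365) = 0.28%, or 0.25 of 90. This bears on the Day 70 points, since people lost earlier have no Day 70 sample in table or figure.

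With the 84-day conversion figures, the plots would miss about 2.2 + 0.25 = 2.4 to 3.8 + 0.25 = 4.0 of 90 at Day 70, and about 2.2 + 1.5 = 3.7 to 3.8 + 1.5 = 5.3 of 90 at Day 0. Isolated missed Day 84 tests would add to this, but the documents give no rate for them.

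**The case against.** The best defence is that the heading has a traceable origin. Protocol 7.1 names an intent-to-treat population for both efficacy and immunogenicity, and SAP 3.3 declares that a modified version replaces it for analysis. SAP 5.2 also calls the Safety set the primary one for immunogenicity, which does not forbid supportive displays on another set. This may explain the wording, but it does not reconcile it. The protocol's intent-to-treat population was everyone randomized, with no Day 84 condition, and SAP 5.3 then gives the modified set to efficacy. SAP 15.1 plans no Safety-set version of these figures, so the primary set would have no plots.

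The defence is right about consequence. The Fisher and Wilcoxon tests, the confidence intervals for medians and the responder percentages are all in Safety-set tables. The difference in treatment grouping matters only if someone received the wrong product, and no such case is documented. The figure shells are not available here, and the missing cohort restriction in the heading is compatible with a drafting slip.

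Three stronger readings are tempting, and the documents do not support them:

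- *The figures show different people from the tables.* They show slightly fewer of the same people.
- *The figures remove precisely the newly infected.* They also drop anyone untested at Day 84. They keep participants whose repeat test is indeterminate, because SAP 14.1.3 deems that result negative, and they keep infected participants who have not yet converted. Some Day 84 positives may be assay variation: Protocol 1.1 cites a 4% false-positive conversion rate in short-term serial testing.
- *The selection biases the comparison between arms.* With 0.7-1.3 converters expected per arm, a 50% vaccine effect acting from Day 0 would make the arms differ by about 0.4-0.6 of a participant (half of 0.72 and half of 1.26). The protocol's own rationale is that Day 84 converters may have been infected before enrolment.

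**Conclusion.** The inconsistency is real and minor. SAP 15.1 plots PBMC ICS data on a set that SAP 5.3 assigns to efficacy, and tabulates and lists the same data on the set that SAP 5.2 names for immunogenicity. The plots would omit about 2-4 Day 84 converters of 90, roughly 1 per arm of 30, plus any participants with no Day 84 test. Plotted medians, quartiles and responder symbols may therefore differ slightly from the tabulated values. Inference and responder percentages are unaffected.

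The size rests on the protocol's annual conversion rates holding at a constant level over the first 84 days. The documents give no Day 84 conversion rate and no rate of missed Day 84 tests, so the counts are illustrative. The mismatch between sets does not depend on them.

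**What to change.** In SAP 15.1, replace the population in the figure heading with the one used for the tables: the Safety set, in the Safety and Immunogenicity Cohort. This aligns participants and treatment grouping across tables, figures and listings, and restores the cohort restriction that the figure heading lacks. If modified ITT figures are also wanted, add them as labelled supplementary output with n per arm.

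The cost is one phrase in the SAP and a changed population filter and treatment variable in the figure programs, with the shells updated to match. No sample size, test or table changes.

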### 15.1.1. DERIVATIONS

#### 15.1.1.1. Negative control-subtracted Cytokine Response

The negative control results are sometimes referred to as the background data. For all immunology presentations, the negative control results are subtracted from the active stimulation antigen results. This result is referred to as the negative control-subtracted response.

#### 15.1.1.2. Single Positive CD107a

The single positive CD107a cytokine combination (for example: APBNGN2N4N17NTN or APBNGN2N17N22NTN), per antigen, is excluded entirely from the Analysis Data Model (ADaM) ICS Result (ADZI) dataset.

Since there are 126\* cytokine combinations (128\* cytokine combinations in total, excluding the all negative and the single positive CD107a cytokine combinations) available to be presented on a polyfunctional figure, it would not be possible to present all combinations on a single figure. Therefore, a subset of four cytokines is to be presented on one figure. The figure presenting the IFN-g, IL-2, TNF and CD107a subset only include 14 polyfunctional combinations on the x-axis instead of the usual 15 combinations, since the last column (IFN-g - IL-2- TNF- CD107a+) is omitted from the figure.

#### 15.1.1.3. Total Number of Cells

The ICS Total number of cells per participant, per day, per T cell, per antigen does include all 128\* cytokine combinations, therefore the single positive CD107a cytokine combination is included in the ICS Total number of cells. The ICS Total number of cells for each cell type is available in the RAW data file and is not recalculated as the sum of all cytokine combinations. The ICS Total number of cells from the RAW dataset:

- Time/Singlets/Viable CD3+/Lymphocytes/Aggregate 1/Aggregate 2/CD4+,Count for CD4.
- Time/Singlets/Viable CD3+/Lymphocytes/Aggregate 1/Aggregate 2/CD8+,Count for CD8.

#### 15.1.1.4. ANY Response

The 'ANY' (%) result per participant, T cell type, stimulation antigen and visit are derived as:

- $\sum$  Cell percentages (%) that respond (positive) at the cytokine level.

The single positive CD107a and all negative combinations should be excluded from this derivation.

#### 15.1.1.5. Total Stimulation Antigen Result

The total stimulation antigen result per participant, T cell type and visit is derived as:

- $\sum$  'ANY' (%) results of Ag85B and TB10.4 antigens (excluding negative control and BCG).

---

Document: Aeras\_C-040-404\_SAP\_V2\_0  
Author: [name]

Version Number: 2.0  
Version Date: 29SEP2017

Template No: CS\_TP\_BS016 – Revision 3  
Effective Date: 01May2012

Reference: CS\_WI\_BS005

#### 15.1.1.6. Positive (G,2)

The 'Positive (G,2)' (%) result per participant, T cell type, stimulation antigen and visit is derived as:

- $\sum$  Cell percentages (%) where IFN – g and/or IL – 2 are positive.

#### 15.1.2. RESPONDER STATUS

To determine the responder status the following steps will be followed:

- Per participant, T cell type, stimulation antigen (including negative control) and visit, derive:
  - o Positive (G,2).
  - o Negative (G,2):
    - Total Cell Count – Positive (G,2).
  - o The applicable cytokines are: IFN-g (G) and IL-2 (2).
- These results and the negative control results (positive and negative cell counts) will then be compared at each visit per participant, T cell type and stimulation antigen, using the Fisher's EXACT test (refer to Section 5.8.5: Fisher's Exact Test in the Figure guidelines).
- P-values will be adjusted for multiplicity by using PROC MULTTEST (Holm Method). The p-values are adjusted across antigens, therefore at a T cell type, by visit-level for each participant.
- Step 1: Determine whether the number of cells responding to the active antigen stimulation is statistically significantly more than the number of cells responding to the negative control stimulation at Baseline (Day 0).
  - o One-sided adjusted p-value  $\geq 0.05$  indicates that the number of cells responding to the active antigen stimulation is not statistically more than the number of cells responding to the negative control stimulation.
    - Participant is classified as a non-responder at Baseline (Day 0).
  - o One-sided adjusted p-value  $< 0.05$  indicates that the number of cells responding to the active antigen stimulation is statistically more than the number of cells responding to the negative control stimulation.
    - Participant is classified as a responder at Baseline (Day 0).
- Step 2: Determine whether the number of cells responding to the active antigen stimulation is statistically significantly more than the number of cells responding to the negative control stimulation, at Day 70.
  - o One-sided adjusted p-value  $\geq 0.05$  indicates that the number of cells responding to the active antigen stimulation is not statistically more than the number of cells responding to the negative control stimulation.
    - Participant is classified as a non-responder at Day 70.
  - o One-sided adjusted p-value  $< 0.05$  indicates that the number of cells responding to the active antigen stimulation is statistically more than the number of cells responding to the negative control stimulation.
    - Participant is classified as a responder at Day 70.

---

Document: Aeras\_C-040-404\_SAP\_V2\_0  
Author: [name]

Version Number: 2.0  
Version Date: 29SEP2017

Template No: CS\_TP\_BS016 – Revision 3  
Effective Date: 01May2012

Reference: CS\_WI\_BS005

- Determine the responder status post-Baseline when taking Baseline (Day 0) into account:

Baseline (Determined in Step 1)	Day 70 (Determined in Step 2)	Responder Status
Non-responder	Non-responder	Non-responder
Non-responder	Responder	Responder
Responder	Non-responder	Non-responder
Responder	Responder	Determine responder status by means of the odds ratio

- Determine the odds ratio for results at Baseline. If the negative control positive count is zero, the odds ratio will be undefined. In these cases the positive negative control count should be imputed to 1 in order to determine an odds ratio.
- Determine the odds ratio for results at Day 70. If the negative control count is zero, the odds ratio will be undefined. In these cases the positive negative control count should be imputed to 1 in order to determine an odds ratio.
- Perform the Breslow-Day test:
  - Test for homogeneity of odds ratio at Day 70 and Baseline (Day 0).
  - P-value  $\geq 0.05$  indicates that the odds ratio at Baseline (Day 0) and Day 70 do not differ statistically significantly.
    - Participant classified as a non-responder at the relevant post-Baseline visit.
  - P-value  $< 0.05$  indicates that the odds ratio at Baseline (Day 0) and Day 70 visit differ statistically significantly.
    - Difference in log odds ratio should be evaluated in order to determine the responder status at Day 70.
- Calculate the difference in the log of the odds ratios at Day 70 and Baseline (Day 0).
  - Difference in log odds ratio =  $\log(\text{odds ratio at Day 70}) - \log(\text{odds ratio at Baseline [Day 0]})$ .
- Determine the responder status based on the Breslow-Day and difference in log odds ratio for cases where the Baseline (Day 0) and Day 70 visit was determined as responders:

Breslow-Day test p-value	Difference in log odds ratio	Responder status
$\geq 0.05$	$< 0$	Non-responder
$\geq 0.05$	$> 0$	Non-responder
$< 0.05$	$< 0$	Non-responder
$< 0.05$	$> 0$	Responder

The aforementioned steps will be implemented to determine the data record-level response per participant, T cell type, stimulation antigen (excluding negative control) and visit. In order to determine the response per participant at a day-level and therefore across T cell type and stimulation antigen, the following conventions will be used:

- Per participant and visit, if all records have a record-level responder status of non-responder, the day level responder status is determined as a non-responder.

Document: Aeras\_C-040-404\_SAP\_V2\_0

Author: [name]

Version Number:

2.0

Version Date:

29SEP2017

Template No: CS\_TP\_BS016 – Revision 3

Reference: CS\_WI\_BS005

Effective Date: 01May2012

Copyright © 2012 Quintiles Transnational Corp. All rights reserved.

The contents of this document are confidential and proprietary to Quintiles Transnational Corp. Unauthorized use, disclosure or reproduction is strictly prohibited.

- Per participant and visit, if at least one of the records has a record-level responder status of responder, the day-level responder status is determined as responder.

The overall responder status is determined as a single responder status per participant across T cell types, stimulation antigens and visits and the following conventions will be used to determine the overall responder status:

- Per participants, if all days have a day-level responder status of non-responder the overall responder status is determined as non-responder.
- Per participants, if at least one of the days has a day-level responder status of responder, the overall responder status is determined as responder.

As the Baseline responder status is used to determine the post-Baseline responder status, it might be possible that not all participants have sufficient data at Baseline (Day 0) or the relevant post-Baseline visit (Day 70) to determine the responder status. These participants will be presented in the figures by means of a different symbol (i.e. triangle) to indicate that the responder status could not be determined.

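### The overall ICS responder status counts pre-vaccination (Day 0) responses, and one row of the responder table declares a response without testing the change from Day 0

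*SAP*

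**What the plan says.** The rule in SAP 15.1.2 has three layers.

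- **Per visit.** Positive and negative cell counts under antigen and under negative control are "compared at each visit per participant, T cell type and stimulation antigen, using the Fisher's EXACT test". A one-sided adjusted p-value below 0.05 makes the record a responder. On multiplicity: "The p-values are adjusted across antigens, therefore at a T cell type, by visit-level for each participant". Step 1 gives Day 0 its own responder or non-responder status and Step 2 does the same for Day 70.
- **Day 70 taking Day 0 into account.** The instruction is "Determine the responder status post-Baseline when taking Baseline (Day 0) into account", and a four-row table combines the two. The row for a Day 0 non-responder and Day 70 responder reads "Non-responder Responder Responder" (Day 0, Day 70, final status). Only the row in which both days are responders goes on to the Breslow-Day test and the sign of the difference in log odds ratios.
- **Roll-up.** Record-level status exists for each visit. One responding record makes the day a responder. The overall status spans T cell types, antigens and visits, and "if at least one of the days has a day-level responder status of responder, the overall responder status is determined as responder".

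Protocol Table 3-3 schedules both PBMC and whole blood ICS on Day 0 and Day 70 only. SAP 15.2.2 carries the same rule over to whole blood ICS.

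**The concern.** A responder label in a vaccine trial should mean that something changed after vaccination. Two features break that link.

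The roll-up does not exclude Day 0. Inclusion criterion 6 requires earlier BCG vaccination, so a detectable response to BCG antigen before any study injection is plausible in all three arms. Read literally, that response alone settles the overall status, whatever happens at Day 70.

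The second table row treats a significant result on Day 70 beside a non-significant one on Day 0 as evidence of a change. An adjusted p of 0.06 on Day 0 and 0.04 on Day 70 is a response under this row, although the two days may be indistinguishable. The SAP recognises the need for a direct comparison in the fourth row and omits it in the second.

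At stake are the meaning of the overall status in the listings, and how far absolute responder percentages, including placebo's, can be read as vaccine-induced.

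**Working it through.** The documents give no error rate or power for the responder rule, so there is no planned figure to reproduce. The rule was coded as written and applied to simulated participants whose true frequencies are identical on Day 0 and Day 70.

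**Inputs from the documents.** One-sided Fisher test at 0.05; Holm over three antigens (Ag85B, TB10.4, BCG) within T cell type and visit; two T cell types; two visits; 30 participants per arm in the Safety and Immunogenicity Cohort. Records per visit: 3 × 2 = 6.

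**Inputs assumed, because the documents do not give them.** 50,000 to 200,000 cells per condition; background 0.01% to 0.03%; stable antigen-specific excess 0 to 0.05%, plus one case with 0.2% for the BCG antigen only. Each scenario used 10,000 participants. Because positives are rare, Fisher's test was computed in its conditional binomial form (check: 0.01785 against 0.01784 from the hypergeometric).

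**Step 1: nominal limits.** Holm holds the error at 0.05 per T cell type and visit. Treating T cell types and visits as independent, one day gives 1 − 0.95² = 0.0975 and both days give 1 − 0.95⁴ = 0.185.

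**Step 2: unchanged participants, 100,000 cells.** The change-test columns require Breslow-Day p < 0.05 and an increase for every Day 70-significant record.

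| Background / excess | Per record, SAP | Per record, change test | Any of 6 at Day 70, SAP | Any of 6, change test | Overall, Day 0 counted |
|---|---|---|---|---|---|
| 0.01% / 0 | 1.0% | 0.4% | 5.0% | 2.5% | 9.7% |
| 0.01% / 0.01% | 23.3% | 2.4% | 70.2% | 12.7% | 97.9% |
| 0.03% / 0.02% | 25.0% | 2.7% | 72.7% | 13.6% | 99.9% |
| 0.01% / 0.05% | 2.7% | 2.7% | 11.8% | 11.8% | 100% |
| 0.02% / BCG antigen only, 0.2% | 1.8%* | 0.7%* | 10.5% | 7.4% | 100% |

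*Record for an antigen with no signal.

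The last column shows the roll-up fault: once a stable response is present on Day 0, nearly everyone is an overall responder. With 20 background positives per 100,000 cells and one T cell type, the overall figure is 62% to 100% for stable excesses of 10 cells or more.

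The per-record columns show the second-row fault, which is confined to weak stable responses. In the second line of the table, 89% of the moves from non-responder to responder fail Breslow-Day or are not an increase. With no signal the rate stays near 1%. With a strong stable response both days are significant, Breslow-Day applies, and the rate is about 2.5%.

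**Step 3: effect on the arm comparison.** Assumptions: 100,000 cells, 20 background positives, Wald approximation to the change test, two-sided Fisher test at 0.05, 30 per arm. Placebo keeps its Day 0 excess. The vaccine arm rises as shown (cells per 100,000).

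| Excess, Day 0 to Day 70 | Vaccine rate: SAP → stricter | Power: SAP → stricter |
|---|---|---|
| 5 to 25 | 82% → 31% | about 100% → 85% |
| 10 to 30 | 74% → about 25% | 99% → 61% to 69% |
| 15 to 35 | 53% → 21% | 51% → 44% |
| 20 to 40 | 33% → 19% | 14% → 34% |
| 20 to 60 | 49% → 46% | 59% → 99% |

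The 61% to 69% is the spread between separate runs. Requiring the change test everywhere loses power in the first three settings and gains it in the last two.

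**The case against.** The strongest defence is that little of this reaches a planned comparison. The responder table in SAP 15.1 is built by visit, T cell type and antigen, and its Fisher tests do not use the any-day roll-up. The SAP names the overall status only in listings. The last paragraph of 15.1.2 says that Baseline is used to derive the post-Baseline status, so Day 0 may have been meant only as a reference. All of that stands, except that an unstated intention does not override wording that says visits and days when Day 0 is one of only two.

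For the second row, the defence is that newly detectable against control is a coherent definition, that one rule applies to all arms, and that the stricter rule discards many true weak responders. This also stands, and it is why the row should not simply be replaced.

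A reader might infer more than the documents support:

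- *That Day 0 responses contaminate the between-arm p-values, or that those tests are invalid.* They do not enter the table, and an identical rule in randomised arms preserves type I error.
- *That the main immunogenicity result is compromised.* Immunogenicity is a secondary objective. Protocol 7.4.1 makes the percentage of responding T cells the primary immune variable, and SAP 15.1 reports change from Baseline and Wilcoxon comparisons without this dichotomy.
- *That the stricter rule would plainly raise power.* With the vaccine rate held at 45%, power is 34% against a 23% placebo rate and 98% against 3%. But the stricter rule lowers the vaccine rate too, as Step 3 shows.

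**Conclusion.** The point holds in two parts of different weight.

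Counting Day 0 in the overall status is a defect in the rule as written. It follows from the text without any simulation: one strong pre-vaccination response makes the overall status positive in any arm. Its reach is the PBMC and whole blood listings. Restricting the status to Day 70 has no downside.

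The missing change test in the second row is a weakness of interpretation, not an error in the randomised comparison. Under the assumed counts, the rule labels about 1% (no signal) to 25% (weak stable response near the detection limit) of unchanged participants responders per antigen, and about 2.5% for strong stable responses. Those rates depend on cell numbers, background and excess that the documents do not state; the logical gap does not. Requiring the change test would lower responder rates substantially for weak responses in all arms, and power could move either way. That supports a sensitivity analysis rather than a replacement.

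**What to change.** 1. In SAP 15.1.2, derive day-level and overall vaccine responder status from Day 70 only. Label the Day 0 result as baseline detectability, not response. Where either visit is missing, set the overall status to undetermined, in line with how the figures already treat such participants.
2. Keep the four-row table for the planned responder analysis. Add a sensitivity version of the responder table in which every Day 70-significant record, whatever its Day 0 result, must also pass the existing Breslow-Day and log-odds-ratio step.
3. State that both changes apply to whole blood ICS through SAP 15.2.2. The sponsor performs that analysis, so two groups will be programming the rule and the wording must leave no choice.
4. Note beside the responder table that absolute percentages under the stated rule include some unchanged participants.

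The cost is SAP wording, minor code and a repeat of the responder table for each derived cytokine combination. No new data or method is needed. Responder rates in the sensitivity table will be clearly lower for weak responses in every arm, and the report should say so in advance.
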